### Study Setting

Study subjects will include all patients who died in an acute care facility in Ottawa (The Ottawa Hospital, Queensway-Carleton Hospital, and Hôpital Montfort) from November 1st, 2019 to August 31st, 2020, and their contacts (as indicated in their medical record). The Virtual support groups will be organized by Bereaved Families of Ontario – Ottawa through a virtual platform.

### Study Participants

We will collect retrospective data from approximately 550 deceased patients. We plan to recruit approximately 200 FMs for the prospective portion of the study with an expected 100 FMs participating in the VSG and 20 FMs in the qualitative interviews. Note that family members will participate in the virtual support group as part of routine care available to them – the support group is not a study-specific intervention, nor will any research team members be involved in the administration of the virtual support group. The scope of the research study related to the virtual support group is to a) inform the 200 bereaved family participants about the support group, so that they may seek out this care available to them and b) conduct qualitative interviews with 20 participants who attended the virtual support group. As such, while we will obtain consent for conducting the qualitative interviews, consent will not be obtained for participation in the virtual support groups.

### Phase 1: Retrospective chart review

We will abstract clinical information from the medical records of all patients who died in an acute care hospital in Ottawa from November 1st, 2019 to August 31st, 2020.

### Data Collection

A trained and experienced research assistant will abstract clinical data related to the patient's admission, including admitting service, sex, gender, admitting source, diagnosis, comorbidities, resuscitative measures, presence of family at or soon before the time of death, comfort medications

ordered/used, and the involvement of the palliative care consultation team. De-identified data will be entered into the secure OHRI Electronic Data Capture System (EDCS) platform to allow consolidated data collection across all participating sites. Data transferred from each site into the EDCS will be limited to non-identifying information, with the exception of age, sex, gender, date of hospital admission (to calculate length of time in hospital), date of death (to calculate hospital length of stay and to establish the amount of time from patient death to when the Phase 2 questionnaires – see below –are completed by family members), and medical history. These variables are required for sub-group data analysis and for inclusion in regression models.

Each site will additionally have a local participant Master File which includes the study ID, patient name, medical record number (MRN), date of birth, and a column indicating whether or not the participant's chart abstraction has been completed and data entered into the online data collection platform (EDCS). Patient name and MRN are needed for data verification and to facilitate accurate chart review. Date of birth is required to calculate age.

Performance Measurement, Health Records, or Decision Support departments at each site will be consulted as needed to assist in data collection and for decedent cohort (i.e. study sample) identification.

## **Phase 2: Prospective Bereavement Data Collection**

We will offer enrolment to the FM contacts indicated in the medical record of each patient who were identified in the retrospective chart review, beginning at minimum 6 months after the death of the patient. A list of FM contact names, phone number, and relationship to the deceased patient will be generated to all research assistants to contact FMs and offer study enrollment. For FMs who agree to enroll (our previous study found a 40-50% enrolment rate), we will collect basic demographic, mental health, and spirituality data similar to our previous work, as well as focused assessments of grief and relationships:

- The Brief Family Relationship Scale (BFRS) to determine closeness of FM to the deceased
- The Inventory for Complicated Grief-revised (ICG-r) to determine the severity of their grief symptoms. Those who enrol will complete the ICG-r at baseline (upon enrollment) and again 6-months later. A recent meta-analysis of psychological interventions for grief suggested that the ICG-r is superior to other grief measurement tools for measuring the effect of bereavement interventions.

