## Abstract

**Background:** Severe grief reactions (SGR), or complicated grief, are experienced by 2-3% of the population after the loss of a loved one, and can be associated with declining health, social distress, increased use of healthcare resources and higher mortality. SGR can be related to the circumstances of the patient at the end of life, particularly in deaths that were unexpected or traumatic, when the family member was unprepared or unsupported. The COVID-19 pandemic has affected many aspects of end-of-life care. For example, infection control measures may reduce interactions between long-term care residents and family members, and have often limited in-person family visiting to the final hours of life, or no visiting at all for patients with COVID-19. Anecdotally, this disruption of normal interactions has been difficult for patients and families alike, and we know that isolation and lack of closure with a loved one can contribute to the risk of SGR. The prevalence of SGR is expected to rise amid increased challenges in supporting a surge of people with SGR due to physical distancing and limited bereavement resources.

**Methods:** The proposed mixed methods explanatory study includes both retrospective and prospective data collection. The quantitative components will principally consist of natural experiments to identify patient/FM characteristics indicating a high risk of SGR during the COVID-19 pandemic. The qualitative components will deepen our understanding of the impact of COVID-19 on bereavement, while providing formative evaluation for the virtual support groups. Study subjects will include all patients who died in an acute care facility in Ottawa (The Ottawa Hospital, Queensway-Carleton Hospital, and Hôpital Montfort) from November 11, 2019 until August 31, 2020, and their primary contact (as indicated in their medical record).

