### Phase 1-3: Quantitative Data Analysis

To address research objectives #1 and #2, we will divide the patients (and FMs) into three groups:

- a. Pre-COVID: Deaths that occurred in an acute care hospital before the impact of the pandemic was first felt in Ottawa (November 1st, 2019–February 29th, 2020): approximately 160 patients.
- b. COVID: Deaths that occurred in an acute care hospital due to COVID-19 (March 1st – August 31st, 2020). Approximately 250 COVID-19 deaths have been reported between January and June 2019 in Ottawa by Ottawa Public Health, of which preliminary data suggest approximately 80 patients died in acute care.
- c. Non-COVID: Deaths that occurred in an acute care hospital between March 1st – August 31st, 2020 but were not COVID-19 related: approximately 160 patients.

To assess the overall impact of the pandemic, we will perform statistical comparisons of clinical and end-of-life care metrics for the Pre-COVID vs. COVID and Non-COVID groups combined. Patients will be matched based on their health and demographic profiles in a 2:1:2 ratio (2 decedents in pre-COVID period: 1 decedent during the pandemic who died of COVID-19: 2 decedents who died during the pandemic of non-COVID-19 causes). We will compare the COVID vs. Non-COVID groups to determine how much of the impact was specifically associated with COVID infection as opposed to the pandemic in general. Pairwise comparisons will be performed using an unpaired t-test or Mann-Whitney test as appropriate for the distribution of the data. We will then also use logistic regression analysis to identify factors associated with an ICG score  $>25$  (i.e. severe scores).

To address research objective #3, we will compare the changes in ICG scores between baseline and 6-months post-baseline for FMs who did versus did not participate in the VSGs (i.e. the difference in differences). This comparison is important since grief symptoms typically improve over time even without intervention. In addition, group allocation is not random and so our analysis may be

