### **RECRUITMENT & CONSENT**

Recruitment will be necessary for the prospective portion of the study that involves family members participation. Family members will be asked to provide verbal consent to provide basic demographic information and complete questionnaires over the phone or secure online platform. Each participant who provides verbal consent will be invited to participate in a virtual support group that is provided by BFO-Ottawa outside of this research study. Family members who participated in the VSG will be invited to participate in a qualitative interview about their experience of the VSG – a separate, additional informed consent form will be provided to these participants. In addition, family members who did not participate in any VSGs will be invited to participate in a qualitative interview enquiring about their reasons for not attending – participants will be reconsented if they choose to take part in these interviews.

We will offer enrolment to the contacts of each patient who were identified in the retrospective chart review. Only family members of patients deceased between November 1st, 2019 to August 31st, 2020 from the three participating sites will be eligible to participate in the study. Contact information (name,

relationship, and phone number) of potential participants will be taken from the FM contacts listed on the deceased patient's medical record. A research staff member will call the bereaved family members to explain the project. Family members will be asked to verbally consent to the first phase of the study which includes the demographic and grief questionnaires.

Following the completion of the questionnaires, participants who are interested in being involved in the subsequent phases of the study will provide phone/video consent to participate in a qualitative interview, and will also provide their address so the research team member can mail the copy of the consent form to the participant.

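### The plan does not settle whether one or several relatives of a decedent may enrol, and the analyses of family members make no allowance for relatives of the same patient

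*Combined protocol and SAP*

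**What the plan says.** Four places in the combined protocol and SAP describe who is approached, and they do not agree.

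- Abstract, Methods: the subjects are the decedents "and their primary contact (as indicated in their medical record", that is, one contact each.
- Study Setting: the parallel sentence reads "and their contacts (as indicated in their medical record".
- Phase 2: "We will offer enrolment to the FM contacts indicated in the medical record of each patient".
- Recruitment & Consent: "We will offer enrolment to the contacts of each patient who were identified in the retrospective chart review".

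No section caps the number of FMs per decedent, gives an order in which contacts are called, or says what happens when two relatives are both willing.

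The section Phase 1-3: Quantitative Data Analysis plans three kinds of analysis. Group comparisons are stated for chart-based clinical and end-of-life measures: "Pairwise comparisons will be performed using an unpaired t-test or Mann-Whitney test". A logistic regression looks for factors associated with an ICG score above 25. A difference in differences with covariate adjustment compares FMs who did and did not attend the VSG. No clustered variance, GEE or random effect appears. The assumptions listed for checking are linearity, collinearity, equal variance and normal residuals. Independence of observations is not on the list.

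**The concern.** Relatives of one patient share the same death, the same chart data and the same study group, and their grief scores are likely to be correlated. A model that counts them as independent overstates the information on any predictor that is constant within the family. Those predictors are central to objectives 1 and 2: period of death, death from COVID-19, and circumstances of the death taken from the chart. The intervals for those odds ratios would be too narrow, and some risk factors would be declared on weaker evidence than the p-value suggests.

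There is also a practical consequence. Research assistants at the three sites work from a contact list, and they could follow either reading and build different samples.

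**Working it through.** **Is there a planned figure to reproduce?** Only a target: "We plan to recruit approximately 200 FMs for the prospective portion of the study with an expected 100 FMs participating in the VSG". The documents give no derivation, power, significance level, standard deviation or intraclass correlation.

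**Count check: FMs enrolled = decedents × enrolment rate × contacts approached per decedent.** Inputs:

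- Decedents: the three groups sum to 160 + 80 + 160 = 400 ("Patients will be matched based on their health and demographic profiles in a 2:1:2 ratio"), whereas Study Participants says "We will collect retrospective data from approximately 550 deceased patients".
- Enrolment rate: 40–50% (Phase 2).

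| Decedents | Contacts approached | At 40% | At 50% |
|---|---|---|---|
| 400 | 1 | 160 | 200 |
| 550 | 1 | 220 | 275 |
| 400 | 2 | 320 | 400 |
| 550 | 2 | 440 | 550 |

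The target of about 200 is reached with one contact per decedent (400 × 50% = 200, or either figure for 550). The count neither requires nor rules out second contacts.

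**Effect on predictors shared within a family.** The share of paired FMs and the intraclass correlation ρ are assumptions. Suppose 40 of the 200 FMs are second contacts: 120 singles plus 40 pairs, from 160 families. With m the number of FMs per family:

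- Σm² / Σm = (120×1 + 40×4) / 200 = 280 / 200 = 1.4
- Design effect DE = 1 + (1.4 − 1)ρ = 1 + 0.4ρ
- True type I error = 2[1 − Φ(1.96/√DE)]
- Effective sample size = 200 / DE

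| ρ | DE | True SE / naive SE | Effective N | True type I error |
|---|---|---|---|---|
| 0.2 | 1.08 | 1.039 | 185 | 5.9% |
| 0.3 | 1.12 | 1.058 | 179 | 6.4% |
| 0.5 | 1.20 | 1.095 | 167 | 7.4% |

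With half as many pairs (20 second contacts, DE = 1 + 0.2ρ) and ρ = 0.3, DE is 1.06 and the type I error 5.7%. With one FM per decedent, DE is 1.00. The formula is for a contrast of means. For the logistic model, ρ refers to the binary severe-score indicator and the result is approximate.

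**Effect on VSG attendance.** The Phase 3 section leaves attendance to each FM, so relatives may differ. In balanced groups, DE = 1 + 0.4ρ if every pair shares attendance and 1 − 0.4ρ if every pair is split. At ρ = 0.3 these are 1.12 and 0.88. A simulated t-test on 200 FMs (6,000 runs per case; simulation standard error √(0.05×0.95/6000) = 0.003) gave type I error as follows:

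- pairs share attendance: 0.066
- attendance random within families: 0.049
- pairs split: 0.036

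**Which analyses are exposed.** The t-test or Mann-Whitney comparisons, as stated, use one chart record per decedent, so a second relative does not affect them. They would be exposed only if also applied to grief scores. The analysis section leaves that open, because it divides FMs as well as patients into the three groups, and objective 1 concerns the bereavement of FMs. The logistic regression and the VSG comparison are at FM level on any reading.

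**The case against.** The best defence is that the plan probably means one FM per decedent. The abstract says so, the target of about 200 fits that reading, and approaching two contacts per decedent would yield 320 or more at the stated rates. The size also rests on two assumed quantities, the documents fix no significance level or primary hypothesis, and objective 3 seeks only preliminary efficacy. Much of this stands, and it limits the point. It does not remove it: the two sections that govern enrolment use the plural without a limit, and the recruitment wording is hard to read as one contact per patient.

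Four stronger readings are tempting, and the documents do not support them.

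- A reader might infer that every listed contact will be enrolled. No section says so; what is shown is an absence of any limit.
- A reader might infer that the target can be met only with second contacts. The count check shows otherwise.
- A reader might infer that every planned test is invalid. The comparisons of care measures are at decedent level, and the VSG model is defined partly by reference to a cited study that cannot be checked here.
- A reader might infer that all FM-level standard errors are too small. That holds for predictors shared within a family. It need not hold in full for personal characteristics such as closeness to the deceased, and for VSG attendance the direction is unknown.

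**Conclusion.** The point holds in a limited form. The documents conflict on the number of FMs per decedent, the enrolment text permits several, and no FM-level analysis provides for it. For predictors shared within a family, the naive standard errors are about 4–10% too small relative to their naive value, and the true type I error is 5.9–7.4%, if 40 of 200 FMs are second contacts and ρ is 0.2–0.5. Neither assumption has a basis in the documents. With fewer pairs the effect shrinks, and with one FM per decedent it disappears. For VSG attendance the naive standard error may be too small or too large. The effect is modest, but the change should be made because it settles both who is called and how the FM-level models are fitted.

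**What to change.** Reconcile the Abstract, Study Setting, Phase 2 and Recruitment & Consent sections in one of two ways.

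1. **One FM per decedent.** State it in all four places with an order of approach, for example the primary contact first and the next listed contact only if the first declines or cannot be reached. The FM-level models then need no change on this account.
2. **Several FMs allowed.** State the rule, and fit all FM-level models (the logistic regression, the VSG difference in differences, and any group comparison of grief scores) with cluster-robust standard errors, GEE, or a random intercept by decedent study ID. If most families contribute one FM, a random-intercept logistic model may be weakly identified, so GEE or robust standard errors are the simpler choice. Report how many decedents contributed more than one FM.

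The decedent study ID already exists in the Phase 1 data collection, so the work is wording plus a variance option in the model. The cost is slightly wider intervals under the second option, or second contacts not enrolled under the first.

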## **Phase 3: Virtual Support Groups**

FMs who participate in the prospective bereavement data collection (i.e. Phase 2) will be invited to attend a virtual support group (VSG) led by Bereaved Families of Ontario- Ottawa (BFO). In pre-COVID times, BFO presented monthly “*Support and Share*” nights with guest speakers, followed by breakout peer support groups for all different types of losses: loss of child, spouse, parent, loss by suicide, etc. These groups are facilitated by trained volunteers with a shared loss and include between 75 and 150 participants. These Support and Share Nights serve as intake sessions- interested participants from the breakout groups can attend “*Closed Groups*” where a smaller group of participants (up to 12) explore their grief more deeply. These run over 8-10 consecutive weeks with the same group of participants. They are led by trained facilitators who have experienced similar losses. Each week has a different theme, based on evidence-based components of bereavement support (e.g. writing a letter to the deceased). The sessions were put on hold in March by the pandemic, but

BFO plans to begin holding these *Closed Groups* by videoconference (these will be the VSGs) again in September 2020.

All participants in the prospective bereavement data collection component of this study will be invited to participate in the VSGs (see approved Virtual Support Group Information Sheet), regardless of the severity of their symptoms. Those with severe symptoms (indicated by an ICG-r score  $>25$ ) will be notified that their symptoms are considered to be severe, with a suggestion to attend the VSGs. A recent meta-analysis of psychological interventions for grief found higher effect sizes in studies of participants who were  $>6$  months post-loss, and those with higher baseline symptom levels. However, no participant in our study will be randomized to any treatment assignment, and the decision to attend the VSG will be left to the FM. Family members will participate in the virtual support group as part of routine care available to them by BFO. The support group is not a study-specific intervention, nor will any research team members be involved in the administration of the virtual support group, and no data will be collected from the virtual support group online sessions. The scope of the research study related to the virtual support group is to a) inform the 200 bereaved family participants about the support group, so that they may seek out this care available to them and b) conduct qualitative interviews with 20 participants who attended the virtual support group (see Phase 4 below). As such, while we will obtain consent for conducting the Phase 2 questionnaires and the Phase 4 qualitative interviews, consent will not be obtained for participation in the virtual support groups. Any participant who expresses suicidal ideation or intention, or other concerning features of severe grief reaction, will be referred for urgent assessment and professional support through their family physician or the emergency department, as per usual practice with BFO.

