confounded by the possibility that people who choose to participate in support groups have more severe symptoms. We will therefore perform an adjusted analysis similar to Newsom et al. in their naturalistic controlled trial of community-based bereavement support. We will estimate an average score for the outcome variable at each time point for the support-group and no-support-group (control) conditions. Where baseline differences in clinical, demographic or loss-related variables exist, these variables will be added as covariates. Assumptions of linearity, multicollinearity, homoscedasticity, and normality of residuals will be tested prior to analysis.

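### The Objective 3 analysis makes no provision for correlation within closed support groups; if that correlation is positive, the standard error of the VSG contrast is understated, by an amount the documents cannot fix

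*Combined protocol and SAP*

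**What the plan says.** The section on Phase 3 (Virtual Support Groups) describes the closed groups as the setting where "a smaller group of participants (up to 12) explore their grief more deeply". It adds "These run over 8-10 consecutive weeks with the same group of participants" and "They are led by trained facilitators who have experienced similar losses". This describes the format before the pandemic. The same section says the closed groups will resume "by videoconference (these will be the VSGs) again in September 2020", so they are the exposure studied in Objective 3.

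Under Study Participants, the protocol states "We plan to recruit approximately 200 FMs for the prospective portion of the study". Of these, about 100 are expected to attend a VSG. That leaves about 100 non-attenders, who belong to no such group.

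The quantitative analysis section compares the change in Inventory of Complicated Grief (ICG) score from baseline to 6 months "for FMs who did versus did not participate in the VSGs (i.e. the difference in differences". It continues: "We will estimate an average score for the outcome variable at each time point for the support-group and no-support-group (control) conditions". Clinical, demographic or loss-related variables that differ at baseline become covariates. Four assumptions are to be tested: linearity, collinearity, constant variance and normal residuals. Independence of observations is not one of them. No section mentions clustering, a group effect, robust standard errors or an ICC.

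Phase 3 also says that nothing will be collected from the online sessions. Phase 2 lists no item on which closed group an FM joined.

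**The concern.** Attenders in one closed group share peers, facilitators and weekly sessions for two months or more. Their changes in ICG score may therefore resemble one another more than those of attenders in different groups. Closed groups may also be organised by type of loss. That is an inference from the loss-specific breakout groups and the matched facilitators; the protocol does not say so. Non-attenders have no such structure, so the comparison is partially nested: clustered in one arm and not in the other.

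An analysis that takes 200 FMs as 200 independent observations would then overstate the information in the attending arm. Any standard error, interval or p-value attached to the preliminary efficacy estimate would be too favourable. The dissemination plan foresees extending the VSGs to other chapters and partner organisations, so that estimate should carry honest uncertainty. Without a group identifier, a suitable model could not be fitted later even if the analysts wanted one.

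**Working it through.** The plan gives no power, precision or sample-size calculation for Objective 3, so there is no figure of its own to reproduce.

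**Inputs from the protocol.** About 100 attenders and, by subtraction from 200, about 100 non-attenders; a ceiling of 12 people per closed group. At that ceiling, 100/12 = 8.3, so at least 9 groups are needed.

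**Inputs assumed.** The documents do not give these:
- ICC of ICG change within a group: 0.02 to 0.10.
- Study FMs per group, m: 2 to 12. At m = 1 there is no effect.
- Equal total variance in the two arms, and a two-sided 5% test.

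**Formulas.**
- Design effect in the attending arm: DE = 1 + (m − 1) × ICC.
- True over naive standard error of the contrast, 100 v 100: R = sqrt((DE + 1)/2).
- True error of a nominal 5% test: 2 × (1 − Φ(1.96/R)).

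**Example.** For m = 6 and ICC 0.05, DE = 1 + 5 × 0.05 = 1.25 and R = sqrt(2.25/2) = 1.061. Then 1.96/1.061 = 1.848, and the error is 6.5%.

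| m | ICC | DE | R | True error |
|---|---|---|---|---|
| 2 | 0.05 | 1.05 | 1.012 | 5.3% |
| 3 | 0.02 | 1.04 | 1.010 | 5.2% |
| 4 | 0.05 | 1.15 | 1.037 | 5.9% |
| 6 | 0.05 | 1.25 | 1.061 | 6.5% |
| 12 | 0.02 | 1.22 | 1.054 | 6.3% |
| 12 | 0.05 | 1.55 | 1.129 | 8.3% |
| 12 | 0.10 | 2.10 | 1.245 | 11.5% |

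Expressed as a shortfall in the naive standard error (1 − 1/R), this is about 1% at m = 3 and ICC 0.02, about 6% at m = 6 and ICC 0.05, and about 20% in the last row.

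**Check by simulation.** Naive t-tests were simulated with attenders in eight groups of 12 and one of 4, against 100 independent non-attenders (20,000 runs). Rejection rates under no effect were 5.0% at ICC 0, 8.3% at ICC 0.05 and 11.7% at ICC 0.10, which agrees with the formula.

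**Power.** With independent observations, 100 v 100 detects 0.396 standard deviations with 80% power. With m = 12, and a test that allows for the clustering, power at that difference is 70% at ICC 0.05 and 61% at ICC 0.10.

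**The case against.** The best counter-argument is that the plan is silent rather than wrong. It names no error structure and no confidence interval, and it says the adjusted analysis will resemble that of a cited naturalistic trial, whose model cannot be checked from these documents. A reader might infer that the interval will certainly be too narrow. The documents do not support that. They support only that no handling of clustering is stated and no identifier is planned; the consequence depends on a positive ICC and on study FMs sharing groups. If the cited model does handle clustering, it would still need the identifier.

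The size is also open. Twelve is a ceiling on everyone in the group. The VSGs are routine care, so groups may include people outside the study, and m could be small. The worst-case row needs every group to be full, made up only of study FMs, and at the top of the assumed ICC range. This objection stands.

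Change scores remove stable differences in severity between groups, and loss-related covariates may absorb some shared variation if they are measured and differ at baseline. Neither removes correlation that arises during the sessions, so this stands only in part.

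A reader might also infer that one unusually strong or weak facilitator could pass for a VSG effect. That goes too far. With 9 or more groups, one full group is at most 12 of 100 attenders, and the protocol speaks of facilitators in the plural.

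Finally, Objective 3 concerns feasibility, acceptability and preliminary efficacy in a self-selected comparison. The plan acknowledges the self-selection, which may be the larger problem. It is a separate one: adjusting for it does not correct the standard error.

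**Conclusion.** The point holds in conditional form. The plan describes a partially nested comparison but provides neither an analysis that recognises it nor the data to support one. If ICG changes are positively correlated within closed groups, and two or more study FMs share a group, the standard error of the VSG contrast is understated. The understatement is negligible with two or three study FMs per group and a low ICC. It is about 6% in a middle case, and in the worst case examined the true standard error is about 1.25 times the naive one. The direction follows from the design; the size rests entirely on the assumed ICC and group composition, and on a roughly 1:1 split. For a preliminary, non-randomised estimate this is a minor issue, worth correcting because it costs little and cannot be repaired once follow-up is over without a group identifier.

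**What to change.** 1. **Record the group.** At the 6-month questionnaire, ask each attender for the group name or, failing that, the start date, meeting day and time, and type-of-loss group. Start month and type of loss alone may not be enough, because the protocol does not rule out parallel groups of the same type. This needs no data from the sessions.

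2. **State the model.** Analyse Objective 3 with a partially nested mixed model: a random group effect among attenders only, with small-sample degrees of freedom. Alternatively, use cluster-robust standard errors with a small-sample correction, treating each non-attender as a cluster of one. Report the estimated ICC and the number of study FMs per group.

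3. **Fallback.** If groups cannot be identified, report as a sensitivity analysis an interval widened by R over a stated range of ICC and m. This shows how far the conclusion depends on clustering but learns nothing about it from the data.

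The cost is one or two extra questions at a contact already planned, a somewhat wider interval, and a group variance that will be imprecise, with perhaps only nine groups if they are full. Recruitment and care are unchanged. Self-selection is not addressed and must still be handled by the adjusted analysis.
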